### **7.6.9 Multiple Events**

See Section 7.6.8 of Core Safety SAP

### **7.6.10 Select Adverse Events**

Unless otherwise specified, analyses will be performed by select AE category. Some analyses may also be repeated by subcategory of endocrine events.

#### **7.6.10.1 Incidence of select AE**

Select AEs will be summarized by treatment group for each category/subcategory:

- Overall summary of any select AEs by worst CTC grade presented by Category or Subcategory/PT (grade 1, 2, 3, 4, 5, unknown)

- Overall summary of any select AEs by worst CTC grade presented by Category or Subcategory/PT (any grade, grade 3-4, grade 5)
- Overall summary of drug-related select AEs by worst CTC grade presented by Category or Subcategory / PT (grade 1, 2, 3, 4, 5, unknown)
- Overall summary of drug-related select AEs by worst CTC grade presented by Category or Subcategory / PT (any grade, grade 3-4, grade 5)
- Overall summary of any serious select AEs by worst CTC grade presented by Category or Subcategory /PT (any grade, grade 3-4, grade 5)
- Overall summary of drug-related serious select AEs by worst CTC grade presented by Category or Subcategory /PT (any grade, grade 3-4, grade 5)
- Overall summary of any select AEs leading to discontinuation by worst CTC grade presented by Category or Subcategory /PT (any grade, grade 3-4, grade 5)
- Overall summary of drug-related select AEs leading to discontinuation by worst CTC grade presented by Category or Subcategory /PT (any grade, grade 3-4, grade 5).

The analyses will be conducted using the 30-day safety window, and some will be repeated using the 100-day safety window.

Summary of frequency of unique select AE by Category will also be reported for each treatment group.

By-subject select AE listing and a select AE definition listing will be provided.

#### **7.6.10.2 Time-to onset of select AE**

Time-to onset of the following specific events will be summarized for each category/subcategory of select AEs for treated subjects who experienced at least one select adverse event from the category/subcategory, reporting median, min, and max:

- Time-to onset of any grade select AE by treatment group
- Time-to onset of grade 3 to 5 select AE by treatment group
- Time-to onset of any grade drug-related select AE by treatment group
- Time-to onset of grade 3 to 5 drug-related select AE by treatment group

See time-to onset definition subsection of [Appendix 1](#) for additional details. The analyses will be conducted using the 30-day safety window.

#### **7.6.10.3 Time-to resolution of select AE**

Time to resolution of the following specific events will be summarized separately for each category/subcategory.

- Time-to resolution of any grade select AE by treatment group
- Time-to resolution of grade 3 to 5 select AE by treatment group
- Time-to resolution of any grade drug-related select AE by treatment group
- Time-to resolution of grade 3 to 5 drug-related select AE by treatment group

- Time-to resolution of any grade select AE where immune modulating medication was initiated, by treatment group.
- Time-to resolution of grade 3 to 5 select AE where immune modulating medication was initiated, by treatment group.
- Time-to resolution of any grade drug-related select AE where immune modulating medication was initiated, by treatment group
- Time-to resolution of grade 3 to 5 drug-related select AE where immune modulating medication was initiated, by treatment group

Time-to resolution analyses are restricted to treated subjects who experienced the specific events. Time-to resolution where immune modulating medication was initiated analyses are restricted to treated subjects who experienced the specific events and who received immune modulating medication during the longest select AE.

See time-to resolution definition subsection of [Appendix 1](#) for additional details. The analyses will be conducted using the 30-day safety window.

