### **5.3.3 Follow-up and Survival Procedures**

The Follow-Up Phase begins when the decision to discontinue a subject from study therapy is made (no further treatment with study therapy).

- Subjects who discontinue treatment for reasons other than tumor progression will continue to have tumor assessments every 8 weeks ( $\pm 1$  week) for the first 13 months from randomization, and every 12 weeks ( $\pm 1$  week) thereafter until documented tumor progression, death, lost to follow-up, or withdrawal of consent.
- Subjects will be followed for drug-related toxicities until these toxicities resolve, return to baseline or are deemed irreversible. All adverse events will be documented for a minimum of 100 days after last dose.
- After completion of the first two follow-up visits, subjects will be followed every 3 months for survival.

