### **6.2.1 Nonserious Adverse Event Collection and Reporting**

The collection of nonserious AE information should begin at initiation of study drug. Nonserious AE information should also be collected from the start of a placebo lead-in period or other observational period intended to establish a baseline status for the subjects.

Nonserious AEs should be followed to resolution or stabilization, or reported as SAEs if they become serious (see [Section 6.1.1](#)). Follow-up is also required for nonserious AEs that cause interruption or discontinuation of study drug and for those present at the end of study treatment as appropriate. All identified nonserious AEs must be recorded and described on the nonserious AE page of the CRF (paper or electronic).

All nonserious adverse events (not only those deemed to be treatment-related) should be collected continuously during the treatment period and for a minimum of 100 days following the last dose of study treatment.

Completion of supplemental CRFs may be requested for AEs and/or laboratory abnormalities that are reported/identified during the course of the study.

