### **6.2.2 Adverse Events of Interest**

IMAEs are specific events occurring within 100 days of the last dose of study drug (which includes pneumonitis, diarrhea/colitis, hepatitis, nephritis/renal dysfunction, rash, and endocrine abnormalities [adrenal insufficiency, hypothyroidism/thyroiditis, hyperthyroidism, diabetes mellitus, and hypophysitis]), regardless of causality, for which subjects received immunosuppressive medication for treatment of the event. The exception to the immunosuppressive medication criteria for IMAEs is endocrine events

(hypothyroidism/thyroiditis, hyperthyroidism, hypophysitis, diabetes mellitus, adrenal insufficiency), which are included regardless of treatment since these events are often managed without immunosuppression.

Per FDA guidance, IMAE analyses included events, regardless of causality, occurring within 100 days of the last dose. These analyses are limited to subjects who received immunosuppressive medication for treatment of the event, with the exception of endocrine events (hypothyroidism/thyroiditis, hyperthyroidism, hypophysitis, diabetes mellitus, adrenal insufficiency), which were included in the analysis regardless of treatment since these events are often managed without immunosuppression.

Table 6.2.2-1 provides a summary of the IMAEs category and their respective PTs.

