#### **6.1.2 Post-baseline period**

On-treatment AEs will be defined as AEs with an onset date-time on or after the date-time of the first dose of study treatment (or with an onset date on or after the day of first dose of study treatment if time is not collected or is missing). For subjects who are off study treatment, AEs will be counted as on-treatment if the event occurred within 30 days (or 100 days depending on the analysis) of the last dose of study treatment. No “subtracting rule” will be applied when an AE occurs both pre-treatment and post-treatment with the same preferred term and grade.

On-treatment evaluations (laboratory tests, pulse oximetry, and vital signs) will be defined as evaluations taken after the day (and time, if collected and not missing) of first dose of study treatment. For subjects who are off study treatment, evaluations should be within 30 days (or 100 days depending on the analysis) of the last dose of study treatment.

Late emergent drug-related AEs will be defined as drug-related AEs with an onset date greater than 100 days after the last dose of study treatment in subjects off study treatment.

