#### **7.6.10.4 Immune Modulating Medication for Select AE**

For each category/subcategory of select AEs, the following will be reported for each treatment group:

- Percentage of subjects who received immune modulating concomitant medication for management of any select AE in the category among subjects who experienced at least one select adverse event in the category/subcategory.
- The total medication treatment duration, duration of high dose of corticosteroid and tapering duration (summary statistics)

These analyses will be performed on any select AEs, drug-related select AEs, grade 3-5 select AEs and drug-related select AEs.

The analysis will be conducted using the 30-day safety window.

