### **Time-to resolution definition**

In order to derive the time-to resolution, overlapping or contiguous AEs within a specific category will be collapsed into what will be termed “clustered” AEs. For example, if a subject (without pre-treatment AE) experienced an AE from 1st to 5th January, another AE (with different PT but within same category) from 6th to 11th January and same AE from 10th to 12th January, these will be collapsed into one clustered AE from 1st to 12th January. [Table 4](#) is summarizing key derivation steps for each type of clustered AEs.

Time-to resolution of AE (any grade) for a specific category is defined as the longest time from onset to complete resolution or improvement to the grade at baseline among all clustered select AEs in this category experienced by the subject. Events which worsened into grade 5 events (death) or have a resolution date equal to the date of death are considered unresolved. If a clustered AE is considered as unresolved, the resolution date will be censored to the last known date alive. Improvement to the grade at baseline implies that all different adverse events in the clustered adverse event should at least have improved to the corresponding (i.e. with same

preferred term) baseline grade. This measure is defined only for subjects who experienced at least one AE in the specific category.

The time-to resolution of AE (grade 3-5) for a specific category is defined similarly with an onset date corresponding to a grade 3-5 AE.

Time-to resolution of drug-related AE (any grade or grade 3-5) is defined similarly but restricted to drug-related AE.

The time-to resolution of AE (any grade or grade 3-5, drug-related or all) where immune modulating medication was initiated is defined similarly with the additional condition that the subject started an immune modulating medication during the longest AE resolution period.

Time-to resolution for a specific subcategory is defined similarly but restricted to event of this subcategory.

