**Table 4: Derivation of clustered AE of interest**

Type of clustered AE of interest	Derivation
Any grade	Collapse any on-treatment AE from the same category
Drug-related of any grade	Collapse any on-treatment drug-related AE from the same category
Grade 3-5	Collapse any on-treatment AE from the same category. Resolution will be based on the onset date of the earliest grade 3-5 records (if no grade 3-5 record, clustered AE is excluded)
Drug-related of Grade 3-5	Collapse any on-treatment drug-related AE from the same category Resolution will be based on the onset date of the earliest grade 3-5 record (if no Grade 3-5 record, clustered AE is excluded)

The algorithm for collapsing adverse event of interest (IMAE, select AE, other event of special interest) records is using the following conventions:

For each subject and specified category, the corresponding adverse event records will be collapsed when:

- 1) Multiple adverse event records have the same onset date.
- 2) The onset date of an event record is either the same day or 1 day later than the resolution date of a preceding event record (contiguous events).

The onset date of an event record is after the onset date and prior to or on the resolution date of a preceding event record (overlapping events).

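### Select AE onset, resolution and medication summaries stop 30 days after last dose, so select AEs starting on days 31–100 enter none of them

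*SAP*

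**What the plan says.** **Window for select AEs.** SAP 7.6.10.2 (onset) and 7.6.10.3 (resolution) close with the same rule: "The analyses will be conducted using the 30-day safety window". SAP 7.6.10.4 (medication) says: "The analysis will be conducted using the 30-day safety window". None of the three provides a 100-day repeat. Only select AE incidence (7.6.10.1) has some tables, not named, repeated at 100 days.

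**What counts.** Under SAP 6.1.2, an AE in a subject off treatment is on-treatment only if it falls within the window used for that analysis. Late emergent events are "drug-related AEs with an onset date greater than 100 days after the last dose of study treatment in subjects off study treatment". For drug-related resolution, Table 4 in Appendix 1 has the rule "Collapse any on-treatment drug-related AE from the same category". A subject's time to resolution is the "longest time from onset to complete resolution or improvement to the grade at baseline among all clustered select AEs in this category".

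**What is collected.** Protocol 6.2.1 collects nonserious AEs during treatment and "for a minimum of 100 days following the last dose of study treatment". Protocol 6.1.1 collects SAEs to 100 days after dosing stops. Protocol 5.3.3 adds: "Subjects will be followed for drug-related toxicities until these toxicities resolve, return to baseline or are deemed irreversible". SAP 7.4.3 takes concomitant medication to 100 days.

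**Parallel sections.** Protocol 6.2.2 says that "IMAE analyses included events, regardless of causality, occurring within 100 days of the last dose", and SAP 7.6.8.1 to 7.6.8.4 apply the 100-day window throughout. For other events of special interest, onset and resolution are partly repeated at 100 days (7.6.11.2, 7.6.11.3) and medication uses 100 days (7.6.11.4).

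**The concern.** The trial collects AEs for at least 100 days after last dose and describes IMAEs over that period, but three select AE sections stop at day 30 and the SAP gives no reason. An event starting on days 31–100 falls between two definitions: too late to be on-treatment in these sections, too early to be late emergent.

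At stake is the description of delayed toxicity that the investigator attributes to nivolumab. A subject whose first drug-related select AE in a category starts on day 45 after last dose is absent from the drug-related onset, resolution and medication summaries. A subject already counted for an earlier event may have a shorter time to resolution on record than the collected data show.

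**Working it through.** The plan gives no figure to reproduce. The check is a reading of the sections against each other, plus simple arithmetic.

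**1. Does an event on days 31–100 enter any of the three summaries?** With a 30-day window it is not on-treatment (6.1.2), so it enters neither the onset nor the medication summary. Table 4 clusters on-treatment AEs only, so it does not enter resolution either. It is not late emergent. The gap is days 31 to 100 inclusive: 100 − 31 + 1 = 70 days.

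**2. How many select AE sets are limited to 30 days?**

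| SAP section | All sets | Drug-related |
|---|---|---|
| 7.6.10.2 onset | 4 | 2 |
| 7.6.10.3 resolution | 8 | 4 |
| 7.6.10.4 medication | 4 | 2 |
| Total | 16 | 8 |

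Seven of the eight drug-related sets are explicit. The eighth rests on reading the last item of 7.6.10.4, which repeats an earlier one, as grade 3–5 drug-related. The eight split into 1 + 2 + 1 = 4 any grade and 4 grade 3–5.

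**3. What do other sections recover?** The 100-day IMAE sections list 4 onset, 2 resolution and 2 medication sets, 8 in all, none of them drug-related. They take in every event that meets the IMAE definition, whatever its cause: listed non-endocrine events given immunosuppression, and listed endocrine events regardless of treatment. Drug-related IMAEs have 2 tables at 100 days, both of incidence (7.6.8.1). The other-events sections have 2 drug-related onset and 2 drug-related resolution sets, of which an unspecified part is repeated at 100 days. Select AEs that are not IMAEs (non-endocrine events without immunosuppression, or terms off the IMAE list) therefore have no onset or resolution summary for days 31–100, unless they are on the other-events list and repeated there.

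**4. How much countable time is lost?** Countable onset time is the time from first to last dose plus the window. The share lost is 70 / (time from first to last dose + 100), with 1 month = 30.4375 days (SAP 8). Months 6 and 12 are assumed examples.

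| Last dose | Calculation | Share lost |
|---|---|---|
| Single dose | 70 / (0 + 100) | 70% |
| Month 6 | 70 / (182.6 + 100) | 24.8% |
| Month 12 | 70 / (365.25 + 100) | 15.0% |
| Month 24 (maximum) | 70 / (730.5 + 100) | 8.4% |

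These are shares of time, not of events. Seventy days is a maximum: a subject who dies or is lost before day 100 loses less, or nothing.

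**5. What happens to time to resolution?** Because the measure is the longest cluster, dropping a later event from a subject already counted can only leave the value unchanged or shorten it. Assumed example: a 14-day drug-related event starts 10 days after last dose, and a separate 60-day one in the same category starts 45 days after it. The 30-day window gives the longest of {14} = 14 days; the 100-day window gives the longest of {14, 60} = 60 days.

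The two drug-related resolution sets limited to events with immune-modulating medication also require that medication was started during the longest event, so membership can change. If only the 14-day event was treated, the subject is in the set at 30 days and out of it at 100. If only the 60-day event was treated, the reverse holds.

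**The case against.** The window is a declared choice. SAP 6.1.2 and Appendix 1 allow 30 or 100 days depending on the analysis, and the SAP gives 100 days to the IMAEs, which carry the primary and secondary endpoints. Select AEs are supportive. Events on days 31–100 may reflect subsequent therapy, which is a fair ground for a 30-day table. All of this stands, and it is why the 30-day tables should stay.

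The overlap with the IMAE tables is also substantial. Four of the eight drug-related sets concern immune-modulating medication, and a listed-category event treated with immunosuppression is an IMAE by definition. For those terms only the drug-related split is missing. How much lies outside the overlap cannot be judged, because the select AE and other-events term lists are not in the documents.

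SAP section 9 places the complete list of analyses in a Data Presentation Plan that is not available here. The point therefore applies to the SAP text; it does not show that the tables will never be produced.

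A reader might infer that these events vanish from the report. The documents do not support that: a by-subject select AE listing is planned, some select AE incidence tables are repeated at 100 days, and drug-related IMAE incidence is tabulated at 100 days.

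The objection does not supply a drug-related onset, resolution or medication summary at 100 days, and it does not explain why only these select AE sections lack any 100-day version.

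**Conclusion.** The point holds as a minor gap in supportive safety summaries. It affects 16 select AE sets, 8 of them drug-related; the drug-related sets matter most because no 100-day IMAE onset, resolution or medication set replaces them. The loss is at most 70 days of countable onset time per subject, and the share is largest for subjects who stop early.

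Two stronger readings are tempting. One is that the trial's main safety result is understated. It is not: the primary and secondary endpoints concern high-grade IMAEs, and SAP 7.6.8 analyses IMAEs at 100 days. The other is that the select AE median times to resolution are biased downwards. That does not follow. The same-or-shorter result is for one subject already counted; across subjects, a wider window also adds new subjects, can add censored times, and can change membership of the medication-initiated sets. The direction for medians, and the number of events affected, cannot be derived, since the documents give no distribution of onset after last dose.

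The conclusion assumes that each section's stated window governs every set it lists, and that the last item of 7.6.10.4 means grade 3–5 drug-related. Without the second assumption, seven drug-related sets remain.

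**What to change.** Keep the 30-day tables. Add to each of SAP 7.6.10.2, 7.6.10.3 and 7.6.10.4 a sentence saying that at least the drug-related analyses, any grade and grade 3–5, will be repeated using the 100-day safety window. Correct the repeated last item of 7.6.10.4 at the same time. State with the 100-day tables that some later events may reflect subsequent therapy, which SAP 7.5.1.3 already summarises; restricting the repeat to drug-related events reduces this problem without removing it.

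Repeating the all-causality sets as well is optional. It would put both versions on the same window and cover events judged not related that are not IMAEs, at the price of eight further sets.

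The cost is one sentence in three sections and a re-run of existing programs for eight sets. No new data and no new definition are needed, since Appendix 1 already allows either window. The downside is a few more supportive tables.

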#### **7.6.10.4 Immune Modulating Medication for Select AE**

For each category/subcategory of select AEs, the following will be reported for each treatment group:

- Percentage of subjects who received immune modulating concomitant medication for management of any select AE in the category among subjects who experienced at least one select adverse event in the category/subcategory.
- The total medication treatment duration, duration of high dose of corticosteroid and tapering duration (summary statistics)

These analyses will be performed on any select AEs, drug-related select AEs, grade 3-5 select AEs and drug-related select AEs.

The analysis will be conducted using the 30-day safety window.

#### **7.6.11 Other Events of Special Interest**

Unless otherwise specified, analyses will be performed by other events of special interest category.

##### **7.6.11.1 Incidence of other events of special interest**

Other events of special interest will be summarized by treatment group for each category:

- Overall summary of other events of special interest by worst CTC grade presented by Category/PT (grade 1, 2, 3, 4, 5, unknown)
- Overall summary of other events of special interest by worst CTC grade presented by Category or Subcategory/PT (any grade, grade 3-4, grade 5)
- Overall summary of drug-related other events of special interest by worst CTC grade presented by Category or Subcategory / PT (grade 1, 2, 3, 4, 5, unknown)

- Overall summary of drug-related other events of special interest by worst CTC grade presented by Category or Subcategory / PT (any grade, grade 3-4, grade 5)
- Overall summary of serious other events of special interest by worst CTC grade presented by Category/PT (grade 1, 2, 3, 4, 5, unknown)
- Overall summary of other events of special interest leading to discontinuation by worst CTC grade presented by Category/PT (grade 1, 2, 3, 4, 5, unknown)
- Overall summary of other events of special interest where immune modulating medication was initiated by worst CTC grade presented by Category/PT (grade 1, 2, 3, 4, 5, unknown)
- Overall summary of other events of special interest where immune modulating medication was initiated by worst CTC grade presented by Category/PT (any grade, grade 3-4, grade 5)
- Overall summary of drug-related other events of special interest where immune modulating medication was initiated by worst CTC grade presented by Category/PT (grade 1, 2, 3, 4, 5, unknown)

The analyses will be conducted using the 30-day safety window, and repeated using the 100-day safety window.

